PMR	Polymyalgia Rheumatica
PP	Per-protocol
QALY	Quality adjusted life year
SAE	Serious adverse event
ROC	Receiver-operator characteristic
TAB	Temporal artery biopsy
TMG	Trial Management Group
TSC	Trial Steering Committee
US	Ultrasound
VAS	Visual analogue scale
VDI	Vasculitis Damage Index
WBC	White blood count

1 Introduction, study design and key trial objectives

1.1 Study outline

The study will assess the performance of ultrasound (US) and temporal arterial biopsy (TAB) in the diagnosis of giant cell arteritis (GCA).

The document was compiled with reference to TABUL protocol version number: 6.0 (Effective date 22 Jan 2013)

This statistical analysis plan is written in conjunction with the International Conference on Harmonisation (ICH) topic E9 (Statistical principles for clinical trials, 1998), applicable standard operating procedures from the University of Sheffield Clinical Trials Research Unit (CTRU) and trial documents referenced in section 6. The trial will be conducted in accordance with Good Clinical Practice (GCP) in Clinical Trials (International Conference on Harmonisation, 1996).

Any deviations from the statistical analysis plan will be described and justified in the final report of the trial. The analysis should be carried out by an identified, appropriately qualified and experienced statistician, who should ensure the integrity of the data during their processing. Examples of such procedures include quality control and evaluation procedures.

1.2 Outcome measures

The objectives of the trial are given in the synopsis below:

Study title	The Role of Ultrasound Compared to Biopsy of Temporal Arteries in the Diagnosis and Treatment of Giant Cell Arteritis (GCA).
Short title	Temporal Artery Biopsy vs Ultrasound in diagnosis of giant cell arteritis (TABUL)
Internal Ref No	REC: 09/H0505/132, HTA: 08/64/01
Study Design	Cohort study (Observational)
Number of Participants	435-445 (in order to achieve 402 participants that have completed the primary end-point at Visit 2 (two weeks))
Primary Objectives	
1. To evaluate the diagnostic accuracy (sensitivity and specificity) of ultrasound as an alternative to temporal artery biopsy for the diagnosis of GCA in patients referred for biopsy with suspected GCA.2. To evaluate the cost-effectiveness (incremental cost per QALY) of ultrasound instead of biopsy in the diagnosis of GCA.
Secondary Objectives	
3. To evaluate inter-observer agreement in the assessment of ultrasound and temporal artery biopsy.4. To elicit expert views on the appropriateness of performing a biopsy following ultrasound using clinical vignettes.5. To evaluate the diagnostic accuracy (sensitivity and specificity) of the sequential diagnostic strategy from 4 as an alternative to temporal artery biopsy alone in the diagnosis of GCA.6. To evaluate the cost-effectiveness (incremental cost per QALY) of the diagnostic strategy from 4 instead of biopsy alone in the diagnosis of GCA.

1.3 Eligibility

The inclusion and exclusion criteria as stated in the protocol are reproduced below:

1.3.1 General considerations

We will adopt a pragmatic approach to recruitment, i.e. aim to include all patients undergoing temporal artery biopsy for suspected GCA. A lower age restriction of 18 will be applied although no age criteria is necessary for this disease type as we expect the majority of patients to be elderly. The clinicians will be using their judgment and clinical experience to determine whether or not to refer for biopsy. We will include patients with pre-existing polymyalgia rheumatica. Most patients will be treated with a standard dose of prednisolone, but some may be commenced on prednisolone plus another immunosuppressive agent. They will be included even though we suspect that the biopsy and scan results may be affected differently than when compared to steroids alone.

1.3.2 Inclusion criteria

For the cohort study

- (1) A clinical suspicion of new diagnosis of GCA e.g. patients with a new onset of headache, scalp tenderness, with or without elevated CRP or ESR, jaw or tongue claudication with or without visual loss.
- (2) The clinician decides that the patient requires an urgent temporal artery biopsy to determine whether or not the diagnosis is GCA.
- (3) The patient agrees and provides NHS consent to undergo a temporal artery biopsy as part of standard care.
- (4) Patients have been started on high dose glucocorticoids or will be started on high dose glucocorticoids.
- (5) Patients must be willing to attend for an ultrasound scan of their temporal and axillary arteries.
- (6) Participants must be willing to give informed written consent or willing to give permission for a nominated friend or relative to provide written informed assent if they are unable to do so because of physical disabilities e.g. sudden onset of blindness/vision loss which can be caused by GCA (this will be made clear in the ethics approval application).
- (7) Must be 18 years of age or

For the training cases

- (1) Patients attending hospital outpatient or in patient departments for assessment for any condition (apart from giant cell arteritis or polymyalgia rheumatica) or healthy staff volunteers.
- (2) Above the age of 50 years.
- (3) Willing to attend for an ultrasound scan of their temporal and axillary arteries.
- (4) Willing and able to give written informed consent.

1.3.3 Exclusion criteria

For the cohort study

- (1) Previous diagnosis of GCA.
- (2) Use of high dose glucocorticoid (>20mg prednisolone/day) for management of current suspected GCA for more than 7 days prior to the dates of the ultrasound and biopsy.
- (3) Long term (>1 month) high dose (>20mg per day at any time) steroids for conditions other than PMR, within three months prior to study entry.
- (4) Inability to give informed consent (either written consent or verbal assent from a relative or carer)
- (5) Inability to undergo an ultrasound scan of the temporal and axillary arteries.
- (6) Patients with a known cause of headache (not due to GCA), or any condition which would preclude the need for a temporal artery biopsy.
- (7) Patients who are unable to undergo an ultrasound scan and a temporal artery biopsy within 7 days of starting glucocorticoids.

For the training cases

- (1) Diagnosis of suspected GCA or a previous history of diagnosed or suspected GCA.
- (2) Inability to give written informed consent.
- (3) Inability to undergo an ultrasound scans of the temporal and axillary arteries

1.4 Randomisation and blinding

No randomisation will be employed: all patients are scheduled to have both TAB and US.

The 2-week visit will be blind to the US findings. If however the assessor intends to withdraw steroids, they contact the TABUL team, who will provide them with the US result. The assessor may choose to continue or withdraw steroids after unblinding the US data. The CRF will capture when this occurs. This procedure ensures that the original diagnosis is based on standard care whilst also allowing additional US findings to protect the safety of the patient.

1.5 Interim analyses, data monitoring committees etc.

Three committees will be established to govern the conduct of this study:

- Trial Management Group (TMG)

This consists of the TABUL study team at the lead site in Oxford (led by the Chief Investigator – [name]) and [name] (Co-Chief Investigator). A list of the TMG is given below:

Name	Function
[name]	Chief Investigator
[name]	Research Nurse
[name]	Co-chief investigator / Statistician
[name]	Research Nurse
[name]	Trial Co-ordinator
[name]	Biomedical Scientist
Miss [name]	Biomedical Scientist
[name]	Ultrasonographer
[name]	IT Manager

- Independent Trial Steering Committee (TSC)

The TSC are an independent group who will provide trial oversight.

Name	Function
[name]	Chair/ Consultant rheumatologist
[name]	Patient Representative
[name]	Clinical Rheumatologist
[name]	Emeritus Professor of General Practice

Members of the TMG may attend DMC meetings as non-voting members.

- Independent Data Monitoring/Management Committee (DMC)

The DMC are an independent committee who, other than offering recommendations to the TSC (primarily around safety to patients), are not involved with the TABUL trial in way. Their membership is as follows:

Name	Function
[name]	Chair/consultant rheumatologist
[name]	Statistician
[name]	Experimental medicine specialist
[name]	Patient representative

Members of the TMG may attend the open section of DMC meetings as non-voting members.

During the study the CTRU will provide the committees with status reports detailing the data completeness, recruitment, loss to follow-up, compliance to protocol and safety outcomes. The remit of the DMC includes recommending that the trial cease on safety grounds, but other than this no interim analyses are planned.

2 Data sources, data and analysis populations

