2.1 Sample Size and Power

A sample of 402 patients provides 90% power at a 5% type I error rate to test the joint hypothesis that

- (i) US has greater sensitivity than TAB, based on detecting a sensitivity of 76% for TAB and 87% sensitivity for US; and
- (ii) The specificity of US is no less than 83%, based on an expected specificity of 96%

The postulated sensitivity and specificity figures are based on the meta-analysis by Karassa et al (2005). This sample size will allow estimation of a one-sided rectangular confidence region for ultrasound false and true positive fractions, assuming 80% prevalence of GCA in patients having a biopsy for suspected GCA, with the sample size inflated ($\gamma=0.1$) due to uncertainty in the proportion of cases/controls in a cohort design (Pepe, 2003).

In order to allow for losses to follow-up the original plan was to recruit 430 participants to the study. It was anticipated that most losses to follow-up will occur in recruited participants not having both ultrasound and biopsy at their appointed time within 7 days of starting steroids. Previous experience of observational studies in PMR (Hutchings et al 2007) suggest no further losses at the

week 2 assessment and 4% at the 6 month assessment. However, the primary outcome (reference standard diagnosis) can be derived in participants who do not complete the 6 month assessment. These assumptions will be checked using early monitoring of recruitment and follow-up rates, with recruitment targets modified as necessary. After monitoring the actual recruitment and withdrawals it was found that the withdrawal rate was slightly higher than expected. It was decided to change the target recruitment figure to 435-445.

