3.4 Efficacy

3.4.1 Accuracy of US and TAB in relation to reference diagnosis (primary endpoint)

The principal outcome is the performance of US and TAB in relation to the reference ('gold-standard') diagnosis of GCA. The reference diagnosis will be reached as specified in the study protocol.

The following summaries will be presented

TAB	The cross-tabulation of diagnosis by TAB against reference diagnosis, together with the sensitivity, specificity, and associated 95% confidence intervals
US	The cross-tabulation of diagnosis by US against reference diagnosis, together with the sensitivity, specificity, and associated 95% confidence intervals
TAB v US	The cross tabulation of diagnosis by TAB against the diagnosis by US, overall and by final reference diagnosis, together with Kappa statistic and the McNemar test

The kappa statistic will be used to assess agreement between TAB and US, and McNemar’s test will be used to detect systematic discordance i.e. whether one method is more or less likely to diagnose (Fleiss *et al* 2003). Rectangular confidence intervals and the McNemar test statistics will be calculated using the exact Binomial methods.

The performance of US will be evaluated as defined in the protocol using a one-sided rectangular confidence region for sensitivity > TAB and specificity > 0.83 with a 5% type I error rate.

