1.4.5 Reference diagnosis evolution and influences

Additional analyses will investigate how the diagnosis changes across the patient's follow-up. The number and percentage of patients whose clinical diagnosis changes between two weeks and six months will be presented, and the characteristics of these patients will be described qualitatively.

The role of various diagnostic tests in reaching the diagnosis of GCA will be reported. Finally, the utility of BVAS and VDI as potential assessment tools for GCA will be investigated using ROC analysis. The BVAS score (range 0-63) is calculated as described in Mukhtyar et al (2009), details of which are provided in Appendix 1; the VDI score (range 0-64) is calculated as described in Exley et al (1997), details of which are provided in Appendix 2.

The following summaries will be presented:

Diagnosis evolution	The number and percentage of patients with a diagnosis of GCA and each alternative diagnosis at two weeks and six months, and the number and percentage of patients whose diagnosis changed between two weeks and six months.
Influences on GCA diagnosis	The proportion of GCA diagnoses which were recorded as being influenced by each of the following: symptoms, signs, blood abnormalities, TAB or other characteristics, at both 2 weeks and 6 months.
Associates with reference diagnosis	The reference diagnosis in relation to various attributes including BVAS and VDI

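### The ultrasound result is released only when steroids are about to be withdrawn, and the CRF record of that release enters no analysis, so a one-directional bias in US accuracy could go unseen

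*SAP*

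**What the plan says.** Section 1.4 sets the default: "The 2-week visit will be blind to the US findings". The exception follows: "If however the assessor intends to withdraw steroids, they contact the TABUL team, who will provide them with the US result". After that, "The assessor may choose to continue or withdraw steroids after unblinding the US data". The event is recorded ("The CRF will capture when this occurs"), and the section gives its reason: "This procedure ensures that the original diagnosis is based on standard care whilst also allowing additional US findings to protect the safety of the patient".

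On the reference standard, section 3.4.1 says only "The reference diagnosis will be reached as specified in the study protocol". Section 2.1 adds that "the primary outcome (reference standard diagnosis) can be derived in participants who do not complete the 6 month assessment". The synopsis in section 1.2 places completion of the primary end-point at Visit 2, two weeks.

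The release record is not mentioned in the major deviations (2.3), the analysis populations (2.4), the primary accuracy analysis (3.4.1), the timing analysis (3.4.3) or the section printed as 1.4.5. That last section plans a table of influences on the diagnosis: "The proportion of GCA diagnoses which were recorded as being influenced by each of the following: symptoms, signs, blood abnormalities, TAB or other characteristics". US is not named in it.

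**The concern.** Release is selective. It reaches patients whom the assessor is about to take off steroids, who are mostly patients heading towards a non-GCA diagnosis. A positive scan can turn that judgement round; a negative scan supports it. Section 1.4 describes no matching release for patients who stay on steroids. If the diagnosis used as the reference is formed or revised after release, the test under study helps to define the standard it is judged against, and it does so in one direction only.

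Both parts of the joint claim in section 3.4.1 are exposed. A US false positive that becomes reference-positive leaves the specificity denominator and enters the sensitivity numerator as a US true positive. If the same patient was biopsy-negative, biopsy loses sensitivity as well. The SAP has arranged to collect the item that would let a reader examine this, and then does not use it.

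**Working it through.** **Inputs from SAP section 2.1.** N = 402; power 90%; type I error 5%; sensitivity 76% for biopsy and 87% for US; specificity 83% (null) and 96% (expected); GCA prevalence 80%; γ = 0.1. The fraction f of US false positives relabelled as GCA after release is not in the SAP. It is an assumption, so a range is shown.

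**1. The plan's own sample size.** For a rectangular region, take α* = 1 − √0.95 = 0.0253 and β* = 1 − √0.90 = 0.0513 on each margin, and n = [(z_α*·√(p0(1−p0)) + z_β*·√(p1(1−p1))) / (p1 − p0)]².
- Cases, 0.76 v 0.87: n = 158.2.
- Controls, 0.83 v 0.96: n = 65.7, so 66.

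At 80% prevalence the controls are binding: 65.7/0.20 = 329. Inflating so that at least 66 controls are obtained with probability 0.95 (γ split over the two margins) gives N = 392, within 3% of 402. With γ = 0.1 on controls alone, N = 377. So the number of non-GCA patients drives the study size, and small movements among them matter.

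**2. Room in the specificity test.** Of 402 patients, about 322 have GCA and 80 do not. With an exact binomial test of specificity > 0.83 at α* = 0.0253, at least 74 of 80 must be US-negative, so at most 6 false positives are allowed. At true specificity 0.83 the chance of passing is 1.2%.

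**3. Effect of relabelling.** With FP = 80(1 − s) and m = f·FP, apparent specificity = (80 − FP)/(80 − m). True negatives do not change and the denominator shrinks, so the value can only rise. Pass probabilities come from the exact binomial for FP, with each false positive relabelled with probability f.

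| True specificity s | FP | f | m | Apparent specificity | P(pass) |
|---|---|---|---|---|---|
| 0.83 | 13.6 | 0 | 0 | 0.830 | 1.2% |
| 0.83 | 13.6 | 10% | 1.4 | 0.844 | 2.9% |
| 0.83 | 13.6 | 25% | 3.4 | 0.867 | 9.8% |
| 0.83 | 13.6 | 50% | 6.8 | 0.907 | 38.9% |
| 0.83 | 13.6 | 75% | 10.2 | 0.951 | 87.5% |
| 0.80 | 16.0 | 0 | 0 | 0.800 | 0.2% |
| 0.80 | 16.0 | 50% | 8.0 | 0.889 | 20.9% |
| 0.96 | 3.2 | 0 | 0 | 0.960 | 95.9% |
| 0.96 | 3.2 | 50% | 1.6 | 0.980 | 99.9% |

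**4. Sensitivity.** Take s = 0.83 and f = 50%, so m = 6.8, and assume all moved patients are biopsy-negative.
- Planned values: US (0.87 × 322 + 6.8)/328.8 = 0.873; biopsy (0.76 × 322)/328.8 = 0.744. The difference goes from 0.110 to 0.128.
- No true difference, both 0.76: US (0.76 × 322 + 6.8)/328.8 = 0.765; biopsy 0.744. A gap of about 2 points appears where there is none.

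**The case against.** The strongest answer is that the decisive step lies outside this document. The bias arises only if the reference diagnosis uses information from after release, and section 3.4.1 hands that rule to the protocol, which may already say how these patients are classified. Two passages point to a reference anchored before release: the synopsis ties the primary end-point to the two-week visit, which is blind to US, and section 1.4 says the original diagnosis rests on standard care. Section 2.1 points the other way only by implication: that the reference can be derived without the six-month visit suggests that the visit is used when available.

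Other points also carry weight. The release rule concerns steroid decisions; the SAP does not say that the recorded diagnosis changes with them. Patients with pre-existing PMR are eligible, so a non-GCA patient might stay on steroids and never trigger release. Some reversals may be correct, where standard care missed true GCA. Section 1.4.5 does report diagnosis changes between two weeks and six months and the role of diagnostic tests, and its category for other characteristics could take in US.

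All of this limits how certain and how large the problem is. A reader might infer that US specificity is inflated and that the primary claim is therefore biased; the SAP does not support that. What stands is narrower. None of the planned summaries separates patients whose US result was released from the rest or repeats the accuracy analysis for them, so correct reclassification could not be told apart from circularity.

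**Conclusion.** The concern holds in conditional form. Selective release, a permitted reversal and an unused record are all stated in the SAP. The direction of any resulting bias in specificity is fixed, and the sensitivity comparison can shift towards US as well. Whether bias occurs depends on the protocol's reference rule.

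Its size depends on an assumed relabelling fraction, on about 80 controls, on treating the relabelled patients as truly non-GCA, and, for the loss of biopsy sensitivity, on their being biopsy-negative. The effect is material if true specificity is near the 0.83 bound and slight if it is near the expected 0.96. Because the specificity criterion turns on about six patients, the check is worth fixing in advance. This is a should-fix point.

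**What to change.** Leave the release procedure and the primary decision rule as they are. Then:

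1. State in section 3.4.1, by reference to the protocol, how patients whose US result was released enter the reference diagnosis.
2. Pre-specify in 3.4.1 a sensitivity analysis of US and biopsy accuracy, including the joint criterion, in which flagged patients keep the diagnosis held before release. The SAP says that the CRF records when release occurs, not that a separate pre-release diagnosis is kept, so this must be confirmed. If it is not kept, exclude flagged patients instead. That is a weaker fallback, since it is likely to remove mainly non-GCA patients, who are already scarce.
3. Report the number flagged and the number whose diagnosis changed after release, each by US result.
4. Add US after release to the influences table in 1.4.5.

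The cost is SAP wording and a few tables. The pre-release diagnosis cannot use later follow-up and would count correct reversals as errors, so it belongs in a sensitivity analysis. Requiring the joint claim to hold under both references would change the decision rule at a power cost that has not been calculated, and is not proposed.

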2.1 Sample Size and Power

A sample of 402 patients provides 90% power at a 5% type I error rate to test the joint hypothesis that

- (i) US has greater sensitivity than TAB, based on detecting a sensitivity of 76% for TAB and 87% sensitivity for US; and
- (ii) The specificity of US is no less than 83%, based on an expected specificity of 96%

The postulated sensitivity and specificity figures are based on the meta-analysis by Karassa et al (2005). This sample size will allow estimation of a one-sided rectangular confidence region for ultrasound false and true positive fractions, assuming 80% prevalence of GCA in patients having a biopsy for suspected GCA, with the sample size inflated ($\gamma=0.1$) due to uncertainty in the proportion of cases/controls in a cohort design (Pepe, 2003).

In order to allow for losses to follow-up the original plan was to recruit 430 participants to the study. It was anticipated that most losses to follow-up will occur in recruited participants not having both ultrasound and biopsy at their appointed time within 7 days of starting steroids. Previous experience of observational studies in PMR (Hutchings et al 2007) suggest no further losses at the

week 2 assessment and 4% at the 6 month assessment. However, the primary outcome (reference standard diagnosis) can be derived in participants who do not complete the 6 month assessment. These assumptions will be checked using early monitoring of recruitment and follow-up rates, with recruitment targets modified as necessary. After monitoring the actual recruitment and withdrawals it was found that the withdrawal rate was slightly higher than expected. It was decided to change the target recruitment figure to 435-445.

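### The 5% type I error is not tied to the sides of the rectangular region: if 5% is the joint region's non-coverage, the both-must-pass test runs at about 2.5% and gives up about 1 to 5 points of power

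*SAP*

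**What the plan says.** Section 2.1 (Sample Size and Power) opens with "A sample of 402 patients provides 90% power at a 5% type I error rate to test the joint hypothesis that", followed by two criteria joined by *and*. The first is greater sensitivity for US than for TAB, "based on detecting a sensitivity of 76% for TAB and 87% sensitivity for US". The second is a US specificity of at least 83%, with 96% expected. On the method, the section says "This sample size will allow estimation of a one-sided rectangular confidence region for ultrasound false and true positive fractions". Prevalence is put at 80%, and the total is described as reached "with the sample size inflated ($\gamma=0.1$) due to uncertainty in the proportion of cases/controls in a cohort design".

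Section 3.4.1 repeats the rule for the analysis: US is judged "using a one-sided rectangular confidence region for sensitivity > TAB and specificity > 0.83 with a 5% type I error rate". It also specifies exact binomial methods for the region and for the McNemar test.

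Section 3.1 sets two-sided 5% tests as the default and exempts one-sided tests of joint hypotheses. It gives no level for those tests. The SAP nowhere states the confidence level of each side of the rectangle.

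**The concern.** Two different quantities can be called 5% here. One is the probability that the joint region misses the true pair of values. The other is the largest probability of declaring success when at least one criterion is false. For a claim that needs both criteria they are not the same. A region with 5% joint non-coverage must have sides tighter than 5%. A both-must-pass test needs no such tightening, because failing either criterion blocks the claim.

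Two things are at stake. First, the stated operating characteristic may describe the region and not the test, in which case power is lost at no gain in the stated error rate. Second, two analysts following section 3.4.1 could set each side at about 97.5% or at 95%, and could reach different primary conclusions from the same data.

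**Working it through.** **Inputs (section 2.1).** Sensitivity 0.76 (TAB) and 0.87 (US); US specificity 0.83 (minimum) and 0.96 (expected); prevalence 0.80; N = 402; 5% type I error; 90% power; γ = 0.1. Assumed, because the SAP does not give them: the level per side, and the discordance between US and TAB among cases.

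**Step 1: size of the both-must-pass test.** The null is that at least one criterion is false. P(pass both) cannot exceed P(pass the false one), which is at most the level of that side. The bound is approached when the other criterion is almost certain to pass. So the maximum type I error equals the level of one side:
- joint 95% region, equal sides: a* = 1 − √0.95 = 0.0253, so the maximum is 2.53%;
- 5% per side: the maximum is 5%.

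Exact methods are discrete and lower these figures further. With exact McNemar and exact binomial tests, independent errors, and averaging over the random number of cases in 402, the joint error at 2.53% per side is about 2.0% when only the sensitivity criterion is false and 1.6% when only the specificity criterion is false. At 5% per side it is about 4% and 3.4%, still below 5%.

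**Step 2: can 402 be reproduced?** Take b* = 1 − √0.90 = 0.0513 and a paired comparison with independent errors. Discordance is 0.87 × 0.24 + 0.76 × 0.13 = 0.3076.

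n = [1.9545 × √0.3076 + 1.6322 × √(0.3076 − 0.11²)]² / 0.11² = (1.0840 + 0.8873)² / 0.0121 = 321.15 cases, and 321.15 / 0.8 = 401.4, i.e. 402.

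This match does not settle the level per side:
- It leaves out the γ = 0.1 inflation. Requiring enough cases with 90% probability gives N = 416.
- Comparing sensitivity with a fixed 0.76 at 2.53% per side needs 159 cases and 66 controls. The controls drive N: 66 / 0.2 = 330, or about 380 with γ = 0.1. Splitting γ to about 0.05 gives 395, and also setting b* = 0.05 gives 400 to 401.
- An unsplit 5% per side in the paired formula gives 403.8 at the maximum possible discordance (0.24 + 0.13 = 0.37) without γ. With γ = 0.1 it gives 395 at discordance 0.35 and 407 at 0.36.

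**Step 3: power at N = 402.** Joint power is the product of the two component powers.

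| Sensitivity comparison | Cases / controls | 2.53% per side | 5% per side | Difference (points) |
|---|---|---|---|---|
| Fixed 0.76, normal approximation | 322 / 80 (expected) | 98.5% | 99.7% | 1.2 |
| Fixed 0.76, normal approximation | averaged over split | 98.2% | 99.6% | 1.4 |
| Fixed 0.76, exact | averaged over split | 96.6% | 98.7% | 2.0 |
| Fixed 0.76, normal approximation | 332 / 70 | 96.4% | 99.2% | 2.8 |
| Paired, discordance 0.20, normal approximation | 322 / 80 | 98.1% | 99.5% | 1.5 |
| Paired, independent errors, normal approximation | 322 / 80 | 93.6% | 97.2% | 3.6 |
| Paired, independent errors, exact | averaged over split | 91.1% | 95.7% | 4.6 |
| Paired, independent errors, normal approximation | 332 / 70 | 92.1% | 97.0% | 4.9 |

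Differences are taken before rounding. An unlucky draw of only 66 controls gives 3.8 points (fixed) or 5.8 points (paired, independent).

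**The case against.** The strongest reply is that the SAP states nothing shown to be false. It gives no level per side, and section 3.4.1 refers to the protocol, which may give one. With 5% per side, the stated 5% is exactly the maximum type I error. With 2.53% per side, 5% is still a valid upper bound and power is still at least 90%. Deciding from a joint region, so that the claim and the reported estimate always agree, is also a legitimate choice. All of this stands. What it does not answer is that the rule leaves the level of its own primary test open.

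Three stronger readings are tempting and are not supported:
- *A reader might infer that N = 402 proves the 5% was split.* It does not. The closest match ignores γ and assumes independent errors, and an unsplit 5% also reaches about 402 at high discordance. Such discordance may be unlikely, but the SAP gives no figure that rules it out.
- *A reader might infer a flat loss of 5 points, or that noticeably fewer patients would do.* Both depend on a paired test with independent errors, an assumption the SAP does not make. Against a fixed 76%, the loss is 1.2 points at the expected split.
- *A reader might infer an inflated false-positive risk.* The direction is the opposite.

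**Conclusion.** The point holds as a conditional one. If the rectangle has 95% joint coverage with equal sides, the 5% in sections 2.1 and 3.4.1 is the region's non-coverage, and the maximum type I error of the joint test is about 2.5%. That reading is natural and consistent with 402, but not proved by it. The test is then conservative and forgoes about 1 to 5 points of power. The lower end applies to a fixed 76% comparator or modest discordance, the upper end to a paired comparison with independent errors. No conclusion of the trial is endangered. The matter is minor, but the level per side should be fixed before the data are seen.

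**What to change.** In sections 2.1 and 3.4.1, separate the test from the region. Either:

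1. Decide each criterion at one-sided 5%, with both required, and report the 95% joint rectangular region as the estimate. This holds the joint type I error at no more than the 5% already stated, adds no patients and raises power. Its cost is that the joint region may touch the null boundary although both tests succeed, and the SAP should say so in advance.
2. If the sponsor confirms that the sides are set at about 2.5% and wishes to keep the region as the decision rule, state the level per side and restate the maximum type I error as about 2.5%. This restatement should not be made without that confirmation, since it would be wrong if the sides are at 5%.

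Both options need only a change of wording in the SAP.
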